3.2 Study Outcome Measures

3.2.1 Primary Outcome Measures

3.2.1.1 The prevalence of electrical dysfunction in the Riata, Riata ST, QuickSite/QuickFlex (1056T, 1058T, 1156T, 1158) and Durata leads.

Lead Population

All enrolled leads within the Riata, Riata ST, QuickSite/QuickFlex (1056T, 1058T, 1156T, 1158) and Durata lead groups.

Analysis:

The prevalence of electrical dysfunction will be calculated as the number of leads that have electrical dysfunction at the time of enrollment in each of the 4 lead groups divided by total number of leads in enrolled patients in each of the 4 lead groups. The one-sided 95% UCB for prevalence will be calculated using Clopper-Pearson exact method.

3.2.1.2 The prevalence of externalized conductors in the Riata, Riata ST, QuickSite/QuickFlex (1056T, 1058T, 1156T, 1158) and Durata leads.

Lead Population

All enrolled leads within the Riata, Riata ST, QuickSite/QuickFlex (1056T, 1058T, 1156T, 1158) and Durata lead groups.

Analysis:

The prevalence of externalized conductors will be calculated as the number of leads that have been shown to have externalized conductors by imaging at the time of enrollment in each of the 4 lead groups divided by total number of leads in enrolled patients in each of the 4 lead groups. The one-sided 95% UCB for prevalence will be calculated using Clopper-Pearson exact method.

3.2.1.3 The prevalence of other visual lead anomalies by each subcategory (fracture, kink, subclavian crush, other irregularities) in the Riata, Riata ST, QuickSite/QuickFlex (1056T, 1058T, 1156T, 1158) and Durata leads.

Lead Population

All enrolled leads within the Riata, Riata ST, QuickSite/QuickFlex (1056T, 1058T, 1156T, 1158) and Durata lead groups.

Analysis:

The prevalence of other visual lead anomalies (by each subcategory) will be calculated as the number of leads that have been shown to have other visual anomaly (by each subcategory) at the time of enrollment in each of the 4 lead groups divided by total number of leads in enrolled patients in each of the 4 lead groups. The one-sided 95% UCB for prevalence will be calculated using Clopper-Pearson exact method.

3.2.1.4 The annual hazard rate of lead electrical dysfunction (from enrollment) by lead subgroups in the Riata, Riata ST, QuickSite/QuickFlex (1056T, 1058T, 1156T, 1158) and Durata leads.

Lead Population

All enrolled leads being followed in this study within the Riata, Riata ST, QuickSite/QuickFlex (1056T, 1058T, 1156T, 1158) and Durata lead groups.

Analysis:

The annual hazard rate will be assessed separately in each of the 4 lead groups along with the subgroups listed in Table 2.

For QuickSite/QuickFlex leads only, data from patients with an additional 1 year of follow-up will contribute to 2 separate lead subgroups (See Section 3.4.5).

3.2.1.5 The annual hazard rate of new cases of externalized conductors (from enrollment), by lead subgroups in the Riata, Riata ST, QuickSite/QuickFlex (1056T, 1058T, 1156T, 1158) and Durata leads.

Lead Population

All enrolled leads being followed in this study within the Riata, Riata ST, QuickSite/QuickFlex (1056T, 1058T, 1156T, 1158) and Durata lead groups.

Analysis:

The annual hazard rate will be assessed separately in each of the 4 lead groups along with the subgroups listed in Table 2.

For QuickSite/QuickFlex leads only, data from patients with an additional 1 year of follow-up will contribute to 2 separate lead subgroups (See Section 3.4.5).

3.2.1.6 The annual hazard rate of new cases of other visual lead anomalies by each subcategory (from enrollment), by lead subgroups in the Riata, Riata ST, QuickSite/QuickFlex (1056T, 1058T, 1156T, 1158) and Durata leads.**Lead Population**

All enrolled leads being followed in this study within the Riata, Riata ST, QuickSite/QuickFlex (1056T, 1058T, 1156T, 1158) and Durata lead groups.

Analysis:

The annual hazard rate will be assessed separately in each of the 4 lead groups along with the subgroups listed in Table 2.

For QuickSite/QuickFlex leads only, data from patients with an additional 1 year of follow-up will contribute to 2 separate lead subgroups (See Section 3.4.5).

3.2.1.7 Prevalence of “other insulation anomalies” in “returned leads” (as defined in section 2.0), by lead subgroups in the Riata, Riata ST, QuickSite/QuickFlex (1056T, 1058T, 1156T, 1158) and Durata leads.**Lead Population**

Any enrolled lead in the study that gets returned to St. Jude Medical for analysis.

Analysis:

The prevalence of “other insulation anomalies” will be calculated as the number of returned leads that have “other insulation anomalies” in each of the 4 lead groups divided by the total number of returned leads in enrolled patients in each of the 4 lead groups. The one-sided 95% UCB for prevalence will be calculated using Clopper-Pearson exact method.

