3.4.1 Enrollment

Upon determination of study eligibility, informed consent will be obtained from eligible patients by the principal investigator or designee prior to initiation of any study related screening activities.

Patients with Riata, Riata ST, QuickSite (1056T or 1058T), QuickFlex (1156T or 1158T), and Durata leads with model numbers and lead implant dates indicated in Table 1 will be screened for evidence of externalized conductors or other visual lead anomalies through cinefluoroscopy that will include three videos/cines of the entire lead length as well as the pocket area (AP, LAO 45° or best possible LAO, RAO 45° or best possible RAO). A copy of Cinefluoroscopy performed as part of separate screening can be used to determine the incidence of externalization as long as all three views (AP, LAO 45° or the best possible LAO view, RAO 45° or the best possible RAO view) are available. Patients who underwent cinefluoroscopy at enrollment as part of the “Riata Lead Evaluation Study” will not be required undergo another baseline cinefluoroscopy. In patients with evidence of externalized conductors, the following chest x-rays will be collected, if available: a) earliest chest x-ray or imaging study showing an evidence of externalized conductors or other visual lead anomalies and b) latest chest x-ray or imaging study that does not show any evidence of externalized conductors or other visual lead anomalies.

Data will be collected on the patient demographics (gender, age, medical history, history of electrical dysfunctions in the past, etc). Lead electrical performance will also be evaluated.

For the purposes of this study, a patient is considered enrolled upon signing of the consent form and collection of data at enrollment visit. Data previously collected from patients enrolled in other ongoing SJM registries may be used for this study.

Data to be captured at enrollment includes:

- RV lead capture threshold, lead pacing impedance and signal amplitude (only required if RV lead model and implant date is listed in Table 1)*
- LV lead capture threshold, lead pacing impedance in a bipolar configuration (only required if LV lead model and implant date is listed in Table 1)
- High Voltage Lead impedance (HVLI) testing – mandatory for Current/ Promote or later ICD and CRT-D, optional for devices before Current/Promote ICD and CRT-D, and not applicable to CRT-P

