11.2 Cinefluoroscopy Adjudication Committee

Cinefluoroscopy Adjudication Committee (CAC) will be comprised of at least three Electrophysiologists or Cardiologists specially trained in using Cinefluoroscopy in this patient population. The role of the CAC is to adjudicate the cinefluoroscopy videos/images to determine the presence of lead compromise in the SJM Cardiac Lead Assessment study patient population. Committee members will be reviewing the cinefluoroscopy videos/images for the enrollment, 12, 24, and 36 month follow-up visits and any additional cinefluoroscopy videos/images received during the course of the study. Data will be sent either electronically or on a disk to the committee members. Once the adjudication is complete, a cinefluoroscopy adjudication form will be collected per patient per study visit. If the presence of externalized conductors is deemed to be ‘indeterminate’ then the cinefluoroscopy will be further reviewed by two other CAC members. Sample pictures/fluoros/x-rays and other examples of “other visual lead anomalies” will be provided to the adjudication committee to aid the committee members in identifying these “other visual lead anomalies” on the cinefluoroscopy videos/images received from the site.

Only the adjudicated imaging data will be included in the post market surveillance reports. Percentage of leads with compromise, evidenced by imaging, will be presented in the report. The type, extent and location of

lead compromise, as described in Appendix A, will also be included. As detailed in Appendix A, each region of the HV as well as CRT leads is divided into different regions. Both the proximal as well as distal ends of externalization will be recorded by the cinefluoroscopy adjudication committee. The distribution of externalization (both absolute number and percentage) by each region of the lead will be presented for both proximal and distal ends of externalization. The distribution of “other visual lead anomalies” (both absolute number and percentage) by each region of the lead and each individual subcategory of “other visual lead anomalies” will be presented. The frequency (both absolute number as well as percentage) of individual subcategories will be reported for “other visual lead anomalies”.

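### The imaging prevalence outcomes (3.2.1.2, 3.2.1.3) count any lead without a determinate adjudicated enrollment read as normal, which lowers the estimate and its upper bound; this is material only where prevalence and the unread share are both appreciable.

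*Combined protocol and SAP*

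**What the plan says.** For externalized conductors, section 3.2.1.2 defines the numerator as "the number of leads that have been shown to have externalized conductors by imaging at the time of enrollment". This is "divided by total number of leads in enrolled patients in each of the 4 lead groups". The stated population is "All enrolled leads within the Riata, Riata ST, QuickSite/QuickFlex (1056T, 1058T, 1156T, 1158) and Durata lead groups". Section 3.2.1.3 uses the same population and denominator for each subcategory of other visual anomaly. Both add the same interval: "The one-sided 95% UCB for prevalence will be calculated using Clopper-Pearson exact method".

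Three other places bear on which leads have a usable read:

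- Section 3.4.1 says "a patient is considered enrolled upon signing of the consent form and collection of data at enrollment visit". It does not mention a readable or adjudicated cine. A cine from separate screening is acceptable only if all three views are available.
- Section 11.2 says that if the presence of externalized conductors is judged indeterminate, "then the cinefluoroscopy will be further reviewed by two other CAC members". It does not say how a lead is classified if the read remains indeterminate, and it describes no further review for other visual anomalies.
- Section 11.2 also says "Only the adjudicated imaging data will be included in the post market surveillance reports".

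**The concern.** The numerator requires a positive adjudicated read. The denominator requires only that the lead belongs to an enrolled patient. A lead whose cine cannot be read, or is still indeterminate after extra review, adds one to the denominator and cannot add to the numerator. Arithmetically it is treated as a lead that was examined and found normal.

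These are primary outcomes answering objectives 1 and 2, in a post-market study carried out under an FDA 522 order. An upper confidence bound is reported so that prevalence is not understated. The written rule can move the estimate and the bound only downward, and it is unbiased only if every unread lead is in fact normal. The bias is a fixed proportion, so a larger sample does not remove it. As the sample grows the interval narrows around a value that is too low.

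**Working it through.** The plan states no expected prevalence, precision target or upper bound for 3.2.1.2 or 3.2.1.3, so there is no figure of its own to reproduce.

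**Inputs from the documents**
- Riata target enrollment in Table 2: 195 + 185 + 180 = 560 leads.
- QuickSite/QuickFlex and Durata: minimum 500 leads, read as 500 per group (section 3.1).
- Reported prevalence of externalized conductors in Riata/Riata ST: 0.5% to 33.3% (section 1.0).
- One-sided 95% Clopper-Pearson bound (section 3.2.1).

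**Assumptions**
- Unread share m of 1% to 10%.
- True prevalence p of 20% for Riata, inside the cited range, and 2% for a 500-lead group.
- Unread leads have the same prevalence as read leads.

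**Formulas**
- With N enrolled leads, n = N(1 - m) read leads and x positives, the planned estimate is x/N = (1 - m)(x/n).
- The upper bound for x out of k is the 0.95 quantile of Beta(x + 1, k - x). The plan uses k = N; the read-lead version uses k = n. Check: for x = 0 and k = 500 it gives 0.597%, which equals 1 - 0.05^(1/500).
- Coverage is the probability, with x distributed Binomial(n, p), that the bound is at or above p.

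**Riata, N = 560, p = 20%**

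| m | n | x | Planned: x/N (bound) | Read leads: x/n (bound) | Coverage of planned bound |
|---|---|---|---|---|---|
| 1% | 554 | 111 | 19.8% (22.8%) | 20.0% (23.0%) | 94% |
| 2% | 549 | 110 | 19.6% (22.6%) | 20.0% (23.1%) | 92% |
| 5% | 532 | 106 | 18.9% (21.9%) | 19.9% (23.0%) | 86% |
| 10% | 504 | 101 | 18.0% (20.9%) | 20.0% (23.2%) | 68% |

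On read leads, coverage stays at 95% to 96% throughout.

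**500-lead group, p = 2%**

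| m | n | x | Planned: x/N (bound) | Read leads: x/n (bound) | Coverage of planned bound |
|---|---|---|---|---|---|
| 2% | 490 | 10 | 2.0% (3.37%) | 2.04% (3.44%) | 97% |
| 5% | 475 | 10 | 2.0% (3.37%) | 2.11% (3.54%) | 96% |
| 10% | 450 | 9 | 1.8% (3.12%) | 2.0% (3.46%) | 95% |

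At p = 0.5% with 500 leads, coverage stays near 100%. With no positives the estimate is 0 under either rule. The planned bound is 0.60%, against 0.66% on 450 read leads.

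**If unread leads differ from read leads.** For Riata at m = 10%, 56 leads are unread. Counting all of them as normal gives 101/560 = 18.0%; counting all as positive gives (101 + 56)/560 = 28.0%. At m = 2% the range is 110/560 = 19.6% to (110 + 11)/560 = 21.6%.

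**The case against.** **Missing cines should be rare.** The three-view cine is to be performed at enrollment (section 3.1), is marked as required in Table 3, and is on the list of material to submit after the enrollment visit (section 3.4.1). Patients carried over from the Riata Lead Evaluation Study skip it only if they already had one at enrollment. A patient with no cine arguably has not met the enrollment definition. This stands, and it narrows the issue mainly to cines that exist but are unreadable or remain indeterminate.

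**The residual may be small.** An indeterminate externalization read goes to two more committee members, and nothing in the documents says that many stay unresolved. This also stands: at m of 1% to 2% the shift is a few tenths of a percentage point even at 20% prevalence.

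**Section 11.2 may already restrict the denominator.** The sentence on adjudicated imaging could be read as limiting the whole percentage to adjudicated leads. But it restricts which reads are reported, whereas 3.2.1.2 and 3.2.1.3 explicitly name all leads in enrolled patients. At best the two sections disagree and need reconciling.

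**Two stronger readings are not supported.** A reader might infer that the bound loses its stated coverage in every lead group. It does not: Clopper-Pearson is conservative, and at low prevalence that margin absorbs the bias. Section 1.0 describes insulation abrasion in Durata leads as extremely uncommon. A reader might also infer that comparisons between lead groups are distorted. Section 3.1 has each group analysed separately, no between-group test is planned for these outcomes, and the documents give no readability rates by lead type.

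**Conclusion.** The concern holds as a definite downward bias in the written rule, of a size the documents do not settle. The planned estimate is (1 - m) times the estimate among read leads, and the upper bound falls with it. With unread leads assumed to resemble read ones, the effect is negligible to small at m of 1% to 2% or at low prevalence. It is material for a high-prevalence group such as Riata: at an assumed 20% prevalence and 560 leads, the nominal 95% bound covers the truth about 86% of the time at m = 5% and 68% at m = 10%. The direction follows from the formula, provided that at least some unread leads have the finding. The magnitude rests on assumed values of m and p.

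**What to change.** 1. In 3.2.1.2 and 3.2.1.3, make the denominator the leads with a determinate adjudicated enrollment read for the finding in question, and compute the Clopper-Pearson bound on that number.
2. In section 11.2, define the final category for a read still indeterminate after further review, say how indeterminate reads of other visual anomalies are handled, and state that the reported percentages use the same denominator as 3.2.1.2 and 3.2.1.3.
3. Report, by lead group, the number of leads excluded and why (no cine, incomplete views, unreadable, still indeterminate).
4. Add a sensitivity range counting every lead without a determinate read first as normal and then as positive. This is needed because the restricted denominator is itself unbiased only if unread leads resemble read ones.

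The cost is wording and tabulation of data the study already collects; no new imaging is required. The downside is slightly smaller denominators and a less favourable estimate and bound.

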3.0 Clinical Protocol

3.1 Study Design and Scope

This study is a prospective, non-randomized, multi-center, international post market study that will determine the prevalence and incidence of externalized conductors and other visual lead anomalies (as evidenced by imaging) and the risk of progression to electrical dysfunction in a large series of ICD/ CRT-D/CRT-P devices containing one or more of the following SJM leads: Riata leads, Riata ST silicone leads, Durata leads, QuickSite/QuickFlex CRT leads. A patient that has at least one market released lead implanted in time period indicated in Table 1 is eligible for enrollment in the study. Each lead group will be considered separately for independent analysis.

Table 1: Leads Eligible for Enrollment

Lead Group	Model Numbers	Lead Implant Date
Riata	1560, 1561, 1562, 1570, 1571, 1572, 1580, 1581, 1582, 1590, 1591, 1592	2002-2009
Riata ST Silicone	7000, 7001, 7002, 7010, 7011, 7040, 7041, 7042	2006-2009
QuickSite/QuickFlex	1056T, 1058T, 1156T, 1158T	2006-2010
Durata	7120, 7121, 7122, 7130, 7131, 7120Q, 7121Q, 7122Q, 7170Q, 7171Q, 7172Q	2008-2010

In order to determine the prevalence and incidence of externalized conductors, other visual lead anomalies as well as electrical dysfunction in the population of leads being evaluated, a minimum of 1500 leads listed above will be enrolled at up to 60 sites. This will comprise a minimum of 300 leads in the Riata lead group and a minimum of 200 leads in the Riata ST lead group to make a combined total of at least 500 Riata and Riata ST silicone leads. The study will also include at least 500 leads in the QuickSite/QuickFlex and Durata lead groups. All patients will be followed every six months for three years.

Adequate representation across the different ages of the leads is also needed to understand the lead population being studied. Therefore, the leads from each group of leads will be compromised of subgroups based on the age of lead (at enrollment) being studied. The required minimum enrollment for each subgroup per lead group is indicated in Table 2. Even if the minimum enrollments indicated in Table 2 are met, extra enrollments may be required to ensure a minimum of 500 leads in each lead group.

Expected Attrition in patients with high voltage leads

Withdrawals due to death

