3.1.1 Projected Study Timeline

A projected timeline for the SJM Cardiac Lead Assessment Study is provided below. Since patients implanted with Riata and Riata ST silicone leads enrolled in the Riata Lead Evaluation Study will be rolled over to this protocol, the timeline takes into the account the initiation of the Riata Lead Evaluation Study done in the 4th quarter of 2011; dates will change based on the date enrollment begins again, and/or the actual enrollment rate.

Time = 0; month 1 September 2011	Time = month 2	Time = month 3	Time = month 4 December 2011	Time = month 5	Time = month 6 February 2012	Time = month 7	Time = month 8	Time = month 9	Time = month 10 June 2012	Time = month 11	Time = month 12 August 2012
Study Initiation			4 site with IRB approval	9 sites with IRB approval	11 sites with IRB approval	17 sites with IRB approval	22 sites with IRB approval	24 sites with IRB approval	24 sites with IRB approval	Enrollment Closed for Riata Silicone Leads	Received FDA 522 Order
			Enrollment = 5	Enrollment = 36	Enrollment = 72	Enrollment = 216	Enrollment = 329	Enrollment = 77	Enrollment = 47		
		Cumulative enrollment	5	41	113	329	658	735	782	Patient follow-up	-----
Time = month 13 September 2012					Time = FDA approval of initial Protocol Rev F February 2013	Time = FDA approval + 1 month	Time = FDA approval + 2 months	Time = FDA approval + 3 months	Time = FDA approval + 4 months	Time = FDA approval + 5 months	Time = FDA approval + 6 months
Protocol Submitted to FDA based on 522 order	//	//	//	//			Enrollments for 522 Order Eligible Leads				29 sites with IRB approval
	//	//	//	//	522 Order eligible enrollments= 720	Enrollment = 4	Enrollment = 56	Enrollment = 66	Enrollment = 77	Enrollment = 126	Enrollment = 128
Patient follow-up	-----	-----	-----	-----	-----	Cumulative enrollment= 724	780	846	923	1049	1177
Time = FDA approval + 7 months	Time = FDA approval + 8 months	Time = FDA approval + 9 months	Time = FDA approval + 10 months	Time = FDA approval + 11 months	Time = FDA approval + 12 months Feb. 2014	-----	Time = FDA approval + 18 months	-----	Time = FDA approval + 24 months Feb. 2015	-----	-----
Enrollment = 168	Enrollment = 80	Enrollment = 58	Enrollment = 36	Enrollment = 16	35 sites with IRB approval Enrollment = 77		43 sites with IRB approval Enrollment = 217		44 sites with IRB approval Enrollment = 135		
Cumulative enrollment = 1345	1425	1483	1519	1535	1612		1829		1964		

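### The upper bounds for prevalence at enrollment ignore site clustering, so their coverage can fall below the stated 95% if prevalence differs between sites

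*Combined protocol and SAP*

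**What the plan says.** Section 3.1 describes the design: "This study is a prospective, non-randomized, multi-center, international post market study". It plans "a minimum of 1500 leads listed above will be enrolled at up to 60 sites" and adds, "Each lead group will be considered separately for independent analysis".

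Sections 3.2.1.1 to 3.2.1.3 define three primary prevalences at enrollment: electrical dysfunction, externalized conductors, and other visual anomalies by subcategory. Each is a crude count of affected leads "divided by total number of leads in enrolled patients in each of the 4 lead groups". The precision statement is the same in all three: "The one-sided 95% UCB for prevalence will be calculated using Clopper-Pearson exact method".

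On how leads fall across sites, the timeline in Section 3.1.1 shows "24 sites with IRB approval" when cumulative enrollment in the predecessor Riata study reached 782, and later "522 Order eligible enrollments= 720". It projects 55 approved sites when Durata and Riata enrollment is complete. No section gives leads per site by lead group, an ICC, a design effect, a cluster-adjusted interval or an analysis by site.

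**The concern.** The Clopper-Pearson bound treats every lead as an independent Bernoulli trial. Leads enrolled at one site may resemble each other in model, age and patient selection, and in implant practice where the site also did the implanting. The introduction reports externalization of 0.5% to 33.3% depending on lead model, and Table 1 pools up to 12 models in a group. Sections 3.2.2.9 and 3.2.2.10 treat venous access, slack and number of other leads as factors worth comparing. Central adjudication of images (Section 11.2) limits differences between readers, but not these.

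The upper bound is the only precision statement planned for these primary prevalences, in a study that answers an FDA 522 order. Positive within-site correlation errs in one direction: it makes the bound too low, so the report would understate how common lead compromise could be.

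**Working it through.** **1. The plan's own figure.** With x affected leads out of n, the bound is U(x) = Beta⁻¹(0.95; x+1, n−x). Its coverage is the total probability of all x with U(x) ≥ p. With independent leads, n from 300 to 825 and p from 0.5% to 33.3%, coverage is 95.0% to 100%. The stated 95% is reproduced, conservatively.

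**2. Leads per site, by lead group.** Group totals are from Section 3.1 and Table 2.

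| Lead group | Minimum / 60 sites | Table 2 target / 55 sites |
|---|---|---|
| Riata | 300/60 = 5.0 | 560/55 = 10.2 |
| Riata ST | 200/60 = 3.3 | 365/55 = 6.6 |
| QuickSite/QuickFlex | 400/60 = 6.7 | 750/55 = 13.6 |
| Durata | 501/60 = 8.4 | 825/55 = 15.0 |

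The 720 rolled-over enrollments came from about 24 sites. Splitting them in the ratio of the Table 2 targets (my assumption) gives 720 × 560/925 = 436 Riata leads, or 18.2 per site, and 284 Riata ST leads, or 11.8 per site. A fair working range is about 5 to 18.

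**3. Coverage with site correlation.** I take k equal sites of m leads, with beta-binomial counts within a site, convolve over sites and apply the rule of step 1. The ICC is assumed. As a guide to its meaning, ICC 0.05 at 15% prevalence is a between-site standard deviation of √(0.05 × 0.15 × 0.85) = 0.08, or 8 percentage points. Coverage (%) for prevalence of 10 to 20%:

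| Sites × leads | ICC 0.01 | ICC 0.02 | ICC 0.05 | ICC 0.10 |
|---|---|---|---|---|
| Riata, 60 × 5 | 95.1–95.6 | 94.8–95.3 | 93.8–94.4 | 92.3–92.9 |
| QuickSite/QuickFlex, 55 × 14 | 94.0–94.9 | 92.9–94.0 | 90.0–91.2 | 85.9–87.3 |
| Durata, 55 × 15 | 93.9–94.6 | 92.8–93.5 | 89.7–90.5 | 85.4–86.4 |
| Riata, 24 × 18 | 94.1–94.9 | 92.8–93.6 | 89.2–90.2 | 84.4–85.4 |

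Unequal site sizes lower these figures. Simulation at ICC 0.05 gives about 86–88% for Riata (436 leads, 24 sites) and about 87–94% for the other groups. Strongly unequal sizes (coefficient of variation 0.8, assumed) take Riata at 24 sites to 83–86%.

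**4. Rare outcomes.** With no events the bound is 1 − 0.05^(1/n), which is 0.60% for n = 500 and 0.99% for n = 300. Any true prevalence below that is covered 100% of the time, whatever the ICC.

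**5. Effect on the bound.** The design effect is DEFF = 1 + (m−1) × ICC, and the bound is recomputed on n/DEFF.
- Riata, 20% of 436, ICC 0.05: DEFF = 1 + 17.2 × 0.05 = 1.86. The bound moves from 23.4% to 24.8%, and to about 25.0% with degrees of freedom of sites minus 1.
- 50 of 500, m = 10, ICC 0.05: DEFF = 1.45, and the bound moves from 12.49% to 13.07%.
- The same at ICC 0.01: DEFF = 1.09, and the bound moves from 12.49% to 12.61%.

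**The case against.** The strongest reply is that this is a general multi-center caveat with little consequence. No hypothesis test, performance goal or decision threshold uses the bound, and the corrected bound is only slightly higher. Both statements are true. They limit the weight of the point but do not remove it, because the bound is still reported as a 95% limit.

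Four stronger readings are tempting, and the documents do not support them.

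- **Coverage is below 95% as a matter of fact.** That needs a positive ICC, and none is given. Clopper-Pearson is conservative enough to absorb ICC 0.01 at 10 leads per site (95.0–96.7% for prevalence of 1% to 33.3%). With Riata ST at its minimum (200 leads, 55 sites), simulated coverage at ICC 0.05 and 10% prevalence is still 95.4%. The documents also do not say that implant factors are set by the enrolling site; leads were implanted from 2002 to 2010, before enrollment.
- **Sites hold about 30 leads each.** This is 720/24, which pools Riata and Riata ST, whereas the bound is computed per lead group. The 24 sites are also an early snapshot.
- **All three outcomes are affected alike.** Section 2.0 ties electrical dysfunction to leads that were capped, extracted or electrically abandoned. It may be very rare at enrollment, and then no shortfall arises.
- **Returned leads (Section 3.2.1.7) are affected too.** The wording of the bound is the same, but the number of returned leads and their spread over sites are unknown, so no size can be given.

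The adjusted bound is not perfect either. With no clustering and 24 sites it over-covers, at about 97%. This is a reason to report it beside the planned bound.

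**Conclusion.** The point holds as a conditional one. Sections 3.2.1.2 and 3.2.1.3, and 3.2.1.1 if events are not very rare, use a bound that assumes independent leads in a study that enrolls by site, and the plan makes no allowance for this. If prevalence differs between sites, coverage can fall below 95%: to about 91–96% at ICC 0.02 and about 86–94% at ICC 0.05. These ranges assume about 5 to 18 leads per site per lead group, prevalence of 10–20% and a beta-binomial model. The ICC values, the split of the 720 enrollments and the site-size distributions are assumptions, not document figures. Below a prevalence of about 0.5–1% there may be no shortfall. The change is worth making because the error runs in one direction and the remedy is cheap.

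**What to change.** In Sections 3.2.1.1 to 3.2.1.3, keep the planned bound and add wording such as: *A site-cluster-adjusted one-sided 95% upper bound will be reported alongside, using the Clopper-Pearson method on the effective sample size n/DEFF (Korn-Graubard). DEFF will be estimated from between-site variation and will not be taken below 1, with degrees of freedom equal to the number of sites minus 1. When there are no events, the unadjusted bound will be kept. Any statement of how high prevalence could be will rest on the higher of the two bounds.*

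In simulation at ICC 0.05 and prevalence of 10–20% the adjusted bound covers about 94–96%. The cost is a slightly higher reported bound: about 0.1 to 0.5 percentage points if there is no clustering, and about 0.5 to 2 points at ICC 0.05. It needs the enrolling site of each lead and a few lines of code, with no extra patients, imaging or visits.
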